16.3. CLASSIFICATION OF AN ADVERSE EVENT

16.3.1. SEVERITY OF EVENT

The following guidelines will be used to describe the severity of AEs.

- **Mild** – Events require minimal or no treatment and do not interfere with the participant’s daily activities.

- **Moderate** – Events result in a low level of inconvenience or concern with the therapeutic measures. Moderate events may cause some interference with functioning.
- **Severe** – Events interrupt a participant’s usual daily activity and may require systemic drug therapy or other treatment. Severe events are usually potentially life-threatening or incapacitating.

Of note, the term “severe” does not necessarily equate to “serious.” Severity is a measurement of intensity. Thus, a severe reaction is not necessarily an SAE. For example, a headache may be severe in intensity but would not be serious unless it met one or more of the criteria for a serious adverse event.

16.3.2. RELATIONSHIP TO STUDY TREATMENT

All AEs must have their relationship to study treatment assessed by the clinician who examines and evaluates the participant based on temporal relationship and his/her clinical judgment. The degree of certainty about causality will be graded using the categories below. In a clinical trial, the study product must always be suspect.

- **Definitely Related** – Evidence indicates a reasonable temporal sequence of the event with the study drug administration exists or that the association of the event with study drug administration is unknown and the event is not reasonably supported by other conditions such that:
 - There is a clinically plausible time sequence between onset of the AE and study treatment administration, and/or
 - There is a biologically plausible mechanism for study treatment causing or contributing to the AE, and
 - The AE cannot be reasonably attributed to concurrent/underlying illness, other drugs or procedures.
- **Potentially Related** – Evidence indicates a possible relationship to the study drug such that:
 - The event occurs within a reasonable period of time relative to the treatment that makes a causal relationship possible, but plausible explanations may also be provided by other causes such as other drugs, products, chemicals, underlying disease, environment, etc.
 - The event is possibly related to the study treatment.
- **Not Related** – Evidence indicates no plausible direct relationship to the study drug such that:
 - A clinically plausible temporal sequence is inconsistent with the onset of the AE and drug administration, and/or
 - A causal relationship is considered biologically implausible
 - The AE can be attributed to concurrent/underlying illness, other drugs or procedures.

16.3.3. EXPECTEDNESS

The investigator will determine whether an AE is expected or unexpected. An AE will be considered unexpected if the nature, severity, or frequency of the event is not consistent with the risk information previously described for the study treatment. Expectedness should be determined if the AE is characterized as related to treatment and is serious (met one or more of the criteria for an SAE).

16.3.4. OUTCOME

The clinical outcome of an AE will be characterized as follows:

- Resolved without sequelae
- Resolved with sequelae (specify)
- Death
- Ongoing (i.e., continuing at the time of study discontinuation)
- Unknown

16.3.5. TREATMENT OR ACTION TAKEN

The clinical treatment or action taken from an AE will be characterized as follows:

- None
- Medical intervention
- Surgical intervention
- Unknown
- Other (specify)

16.3.6. ACTION TAKEN WITH INVESTIGATIONAL PRODUCT

The action taken with the IP will be characterized as follows:

- None
- Drug temporarily withdrawn
- Drug discontinued
- Unknown

16.4. TIME PERIOD AND FREQUENCY FOR EVENT ASSESSMENT AND FOLLOW-UP

The occurrence of an AE or SAE may come to the attention of study personnel during study visits and interviews of a study participant presenting for medical care or upon review by a study monitor. At study visits, study personnel should pose general questions to the participant to ascertain if the participant experienced any issues prior to the visit.

All AEs, including local and systemic reactions not meeting the criteria for SAEs, will be captured on the appropriate CRF/eCRF. Information to be collected includes event description, date of onset, clinician's assessment of severity, relationship to study product (assessed only by those with the training and authority to make a diagnosis), and date of resolution/stabilization of the event. All AEs occurring while in the study must be documented appropriately regardless of relationship to the study product.

Any medical condition that is present at the time that the participant is screened will be considered as baseline and not reported as an AE. However, if the study participant's condition deteriorates at any time during the study, it will be recorded as an AE.

Changes in the severity of an AE will be documented to allow an assessment of the duration of the event at each level of severity to be performed.

The investigator or designee will record all reportable events with start dates occurring any time after the study drug is first administered until 7 (for non-serious AEs) or 30 days (for SAEs) after the last day of study participation. At each study visit, the investigator will inquire about the occurrence of AE/SAEs since the last visit. Events will be followed for outcome information until resolution or stabilization.

Whenever possible, recognized medical terms should be used when recording AEs. Colloquialisms and/or abbreviations should not be used. Only one medical concept, preferably a diagnosis instead of individual symptoms, should be recorded as the event (e.g., record congestive heart failure rather than dyspnea, rales and cyanosis). However, if a constellation of signs and/or symptoms cannot be medically characterized as a single diagnosis or syndrome at the time of reporting, each individual sign or symptom should be recorded as a separate AE. A diagnosis that is subsequently established should be reported as follow-up information.

Adverse events occurring secondary to other events (e.g., sequelae) should be identified by the primary cause. A “primary” event, if clearly identifiable, should represent the most accurate clinical term to record as the AE event term. For example: Orthostatic hypotension ⇒ fainting and fall to floor ⇒ head trauma and neck pain. The primary event is orthostatic hypotension and the sequelae are head trauma and neck pain.

16.5. ADVERSE EVENT REPORTING

The investigator must record nonserious adverse events and submit on the CRF/eCRF in a timely manner.

16.6. SERIOUS ADVERSE EVENT REPORTING

The study clinician will immediately report to the sponsor and Medical Monitor any SAE, whether or not considered study treatment-related, including those listed in the protocol or Investigator’s Brochure and must include an assessment of whether there is a reasonable possibility that the study treatment caused the event [21 CFR 312.64(b)]. Serious adverse events must be reported immediately to the below-listed individuals using the Serious Adverse Event Report (SAER) form. Sites will also be instructed to document the event in the Serious Adverse Event eCRF.

All SAEs will be followed until satisfactory resolution or until the site investigator deems the event to be chronic or the participant is stable. Other supporting documentation of the event may be requested by the study sponsor and should be provided as soon as possible.

The study sponsor or designee will be responsible for notifying the Food and Drug Administration (FDA) of any unexpected fatal or life-threatening suspected adverse reaction as soon as possible, but in no case later than 7 calendar days after the sponsor's initial receipt of the information [21 CFR 312.32I(2)]. In addition, the sponsor must notify the FDA and all participating investigators in an Investigational New Drug (IND) safety report of potentially serious risks from clinical trials or any other source as soon as possible, but in no case later than 15 calendar days after the sponsor determines that the information qualifies for reporting [21 CFR 312.32I(1)]. In each IND safety report, the sponsor must identify all IND safety reports previously submitted to the FDA concerning a similar suspected adverse reaction and must analyze the significance of the suspected adverse reaction in light of previous, similar reports or any other relevant information. The sponsor must report any suspected adverse reaction that is both serious and unexpected. The sponsor must report an AE as a suspected adverse reaction only if there is evidence to suggest a causal relationship between the drug and the AE.

16.7. REPORTING EVENTS TO PARTICIPANTS

It will be the responsibility of the principal investigator to inform participants of any AEs or SAEs deemed related to the study drug and of any study-related results.

16.8. REPORTING OF PREGNANCY

Women of Childbearing Potential (WOCBP) includes any females who have experienced menarche and who have not undergone successful surgical sterilization (hysterectomy, bilateral tubal ligation or bilateral oophorectomy) or are not postmenopausal at least 12 months since last menses. WOCBP will be required to use designated methods of birth control during the course of the study. All women who are pregnant, nursing an infant or planning a pregnancy during the duration of this study will be excluded from participation.

If a participant or investigator suspects that the participant may be pregnant prior to study drug administration, the study drug should be withheld until the results of pregnancy testing are available. If pregnancy is confirmed, the participant should not administer the study drug and should not be enrolled in the study.

If a female participant becomes pregnant during the study, use of the study drug should be discontinued immediately. The investigator will notify the sponsor (or designee) immediately after the pregnancy is confirmed. The investigator will (1) obtain a consent from the female participant for pregnancy follow-up and (2) follow the progress of the pregnancy to term. The investigator should document the outcome of the pregnancy and provide a copy of the documentation to the sponsor or designee. The sponsor or sponsor's designee will be responsible for reporting to the IRB and regulatory agencies as appropriate.

17. COMPLIANCE WITH PROTOCOL

Participation in the study will be summarized by presenting the number of participants who received at least one dose of the study treatment, the number of participants who completed the study per protocol, and the number of participants who did not complete the study by reason of early discontinuation.

18. PUBLICATION OF THE RESULTS AND PROTECTION OF COMMERCIAL SECRETS

This study will comply with the Clinical Trials Registration and Results Information Submission rule. As such, this trial will be registered at ClinicalTrials.gov, and results information from this trial will be submitted to ClinicalTrials.gov. In addition, every attempt will be made to publish results in peer-reviewed journals.

A large rectangular area of the page is completely blacked out, indicating redacted content. The redaction is composed of several horizontal lines of varying lengths, creating a stepped effect.

19. DATA COLLECTION AND REPORTING

Source Documentation: Source documentation for this study will be maintained to document the treatment and study course of each participant and to substantiate the integrity of the trial data submitted for review to the regulatory agencies. Source documentation will include, but may not be limited to: Worksheets, hospital and/or clinic or office records documenting participant visits, including study and other treatments or procedures, medical/ophthalmologic history and physical examination information, laboratory and special assessment results, pharmacy records, drug accountability records and medical consultations.

Medical/ophthalmologic history should be recorded for the past [REDACTED] of the participant. Concomitant medications taken by the participant 3 months prior to Day 1 should be recorded.

Case Report Forms: All historical data and required study observations obtained during the study will be entered in the participant's source documentation and transcribed to the appropriate case report forms (CRFs/eCRFs). CRFs/eCRFs will be filled out completely for each participant in accordance with instructions from Tarsus Pharmaceuticals or its designee. The investigator should ensure that all data on the CRF/eCRF is accurate and consistent with the source documents. Only the principal investigator or other designated sub-investigator(s) may sign and date the designated CRF/eCRF page(s).

Clinical Research Protocol

Protocol TRS-008

01-Feb-2023

The CRFs/eCRFs will be monitored and corrected on-site and, if necessary, clarified on an ongoing basis. The site will be queried if any data, signatures or forms are missing or incorrect. Case report forms can be used as source documents where appropriate.

Monitoring and Inspection of Records: The investigator must allow regular inspections of all study records including CRFs/eCRFs, source documents and regulatory documents by the study monitor. This measure is to ensure that the study is carried out and documented in accordance with all regulatory requirements and the terms of this protocol.

In cooperation with the on-site staff, a designated study monitor(s) will:

- Review all study documents to ensure compliance with the protocol
- Review data recordings for each visit to verify the accuracy and completeness of the information on the CRFs/eCRFs against appropriate source documents
- Review drug disposition and accountability records
- Review adequacy of enrollment rate
- Review required regulatory documentation

Record Retention: The investigator is responsible for maintaining adequate records to enable the conduct of the study to be fully documented. This includes:

- The Investigator's Brochure, signed protocol and amendments
- Signed and dated informed consents per institutional policy
- Signed, dated, and completed CRFs/eCRFs and documentation of CRF corrections
- Notification of SAEs and related reports
- All study drug dispensing and accountability logs
- Shipping records of investigational drug and trial-related materials
- Dated and documented IRB protocol approvals and all correspondence between the investigator and IRB
- *Curriculum vitae* and current medical licenses for principal investigator and all sub-investigators

Source documents: The investigator is responsible for maintaining adequate case histories in the source documents of each participant. The following data will be noted by the investigator in the source medical records of each participant enrolled in the study:

- The participant is participating in this clinical trial
- The date the informed consent form was signed
- Kit numbers
- Date of study completion or withdrawal

The investigator must maintain a copy of all study documents for the period of time that is required by the regulatory authorities. No documents will be destroyed without prior written permission from Tarsus Pharmaceuticals.

Clinical Research Protocol

Protocol TRS-008

[figure not shown]
01-Feb-2023

Data Management: The data will be entered into a secure study database. The database will be electronically stored and a copy placed in backup on a regular basis. Case report forms will be stored for reference. Any data inconsistencies will be resolved by a data clarification request and final resolution verified during site monitoring and study closure. Study documents should be retained for a minimum [REDACTED] after the last approval of a marketing application and until there are no pending or contemplated marketing applications or until at [REDACTED] have elapsed since the formal discontinuation of clinical development of the study treatment. These documents should be retained for a longer period, however, if required by local regulations. No records will be destroyed without the written consent of the sponsor. It is the responsibility of the sponsor to inform the investigator when these documents no longer need to be retained.

[figure not shown]
Protocol Amendments: Any amendments to the protocol must be approved by the IRB in advance of implementation.

Deviations from Clinical Investigation Plan: All deviations from the protocol should be clearly documented. Deviations conducted to protect a participant from possible hazards should be reported to the IRB as soon as possible.

Clinical Research Protocol
Protocol TRS-008
01-Feb-2023

[figure not shown]
21. PROTOCOL AMENDMENT HISTORY

Clinical Research Protocol

Protocol TRS-008

[figure not shown]
01-Feb-2023

Clinical Research Protocol

Protocol TRS-008

01-Feb-2023

Clinical Research Protocol

[figure not shown]
Protocol TRS-008

01-Feb-2023

Clinical Research Protocol

Protocol TRS-008

01-Feb-2023

Clinical Research Protocol

[figure not shown]
Protocol TRS-008

01-Feb-2023

Clinical Research Protocol

Protocol TRS-008

01-Feb-2023

Clinical Research Protocol

Protocol TRS-008

01-Feb-2023

2.2.1 Sample Size Justification	7
2.2.2 Schedule of Events	8
2.2.3 Randomization/Masking	9
2.2.4 Study Populations for Analysis	9
2.2.5 Baseline Characteristics/Medical History	10
2.2.6 Subject Disposition	10
2.2.7 Methods for Handling Missing Data	10
2.2.8 Efficacy Analyses	10
2.2.9 Safety Analyses	15
3 DOCUMENT VERSION CONTROL.....	19

CONFIDENTIAL

This document is the property of Clinical Trial Data Services and may not be reproduced without the written permission of the management of Clinical Trial Data Services.

1 Protocol Summary

Title	Randomized, Double-Masked, Pilot Study Comparing the Safety and Efficacy of Two Dosing Regimens of TP-03 for the Treatment of Meibomian Gland Dysfunction in Patients with Demodex Lid Infestation (Ersa)
Test Article	TP-03, lotilaner ophthalmic solution, 0.25%
Other Test Article	Vehicle of TP-03 to maintain masking of BID dosing
Objective	
To evaluate the safety and efficacy of TP-03, 0.25%, BID versus TID dosing for the treatment of meibomian gland dysfunction in patients with Demodex lid infestation.
 
Efficacy will be evaluated by the assessment of lower lid meibomian gland secretion, erythema of the lid margins, [REDACTED]
 
[REDACTED]
 
Safety will be determined by assessing adverse effects related to treatment [REDACTED]
 
[REDACTED]
 
[REDACTED]

Clinical Hypothesis	Treatment with TP-03, 0.25%, TID will result in a greater improvement from baseline than BID treatment for 85 days in the signs [REDACTED] of MGD with no significant increase in ocular irritation.
Study Design	Prospective, randomized, two-arm, double-masked, parallel treatment study
Number of Participants	Up to 40
Participant Population	Participants with evidence of meibomian gland dysfunction in the presence of Demodex infestation
Description of Sites	Up to six sites in the United States
Study Duration	Approximately 9 months
Randomization	1:1
Study Visits	Study visits will take place at Day 1 (Baseline), Day 15, Day 29, Day 43, Day 57 and Day 85
Safety Measures	
 • Adverse events • [REDACTED] • Slit lamp biomicroscopy findings

CONFIDENTIAL

This document is the property of Clinical Trial Data Services and may not be reproduced without the written permission of the management of Clinical Trial Data Services.

Efficacy Measures	
 • Lower lid meibomian gland secretion assessment 
 ○ Total meibomian gland score ■ [REDACTED] ■ [REDACTED] • Lid margin erythema 
 ■ [REDACTED]
Statistical Considerations	
This is a pilot study to compare the safety and efficacy of two different dosing regimens, BID and TID, of TP-03 for the treatment of MGD. There are no prior data available to perform a sample size estimate. The sample size of 40 participants was selected based on clinical and practical considerations.

Statistical Analysis Plan	
Safety measures will be summarized for each treatment regimen and both treatment regimens combined using descriptive statistics.
 
Efficacy measures will be compared between dosing regimens as the change from baseline using either the t-test or Wilcoxon rank-sum test as appropriate. Comparisons will be two-sided using an α of 0.05. No adjustment will be made for multiple comparisons. Additional analyses will be performed examining the change from baseline in the efficacy measures for both treatment regimens combined.

2 Statistical Methodology

[figure not shown]
[figure not shown]
[figure not shown]
[figure not shown]
[figure not shown]
[figure not shown]
[figure not shown]
[figure not shown]
2.1 General Considerations

The objective of this study is to evaluate the safety and efficacy of TP-03, 0.25%, for the treatment of MGD in participants with Demodex lid infestation. Efficacy outcomes will include:

CONFIDENTIAL

This document is the property of Clinical Trial Data Services and may not be reproduced without the written permission of the management of Clinical Trial Data Services.

- Total meibomian gland secretion score (MGSS) computed as the sum of the grades for all 15 glands evaluated on the lower eyelid with a range from 0 to 45

[figure not shown] 0 \end{aligned}$$

where D is the improvement from baseline

Note for measures where an improvement from baseline would be a decrease from the baseline score these hypotheses are inverse.

$$\begin{aligned} H_0: D &\geq 0 \\ H_A: D &< 0 \end{aligned}$$

where D is the improvement from baseline

2.2.9 Safety Analyses

Safety analyses will be conducted on the Safety Population. Only descriptive statistics will be presented; inferential statistical testing will not be performed.

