**Randomized, Double-Masked, Pilot Study Comparing the Safety and Efficacy
of Two Dosing Regimens of TP-03 for the Treatment of Meibomian Gland
Dysfunction in Patients with *Demodex* Lid Infestation (Ersa)**

Protocol Number: TRS-008

[REDACTED]

[REDACTED]

[REDACTED]

[REDACTED]

IND Sponsor: Tarsus Pharmaceuticals, Inc.

NCT05454956

PROTOCOL SUMMARY

TITLE	Randomized, Double-Masked, Pilot Study Comparing the Safety and Efficacy of Two Dosing Regimens of TP-03 for the Treatment of Meibomian Gland Dysfunction in Patients with Demodex Lid Infestation (Ersa)
TEST ARTICLE	TP-03, lotilaner ophthalmic solution, 0.25%
OTHER TEST ARTICLE	Vehicle of TP-03 to maintain masking of BID dosing
OBJECTIVE	
To evaluate the safety and efficacy of TP-03, 0.25%, BID versus TID dosing for the treatment of meibomian gland dysfunction in patients with Demodex lid infestation.
 
Efficacy will be evaluated by the assessment of lower lid meibomian gland secretion, erythema of the lid margins, [REDACTED], [REDACTED].
 
Safety will be determined by assessing adverse effects related to treatment [REDACTED]
 
[REDACTED]

CLINICAL HYPOTHESIS	Treatment with TP-03, 0.25%, TID will result in a greater improvement from baseline than BID treatment for 85 days in the signs [REDACTED] of MGD with no significant increase in ocular irritation.
STUDY DESIGN	Prospective, randomized, two-arm, double-masked, parallel treatment study
NUMBER OF PARTICIPANTS	Up to 40
PARTICIPANT POPULATION	Participants with evidence of meibomian gland dysfunction in the presence of Demodex infestation
DESCRIPTION OF SITES	Up to six sites in the United States
STUDY DURATION	Approximately 9 months
RANDOMIZATION	1:1
STUDY VISITS	Study visits will take place at Day 1, Day 15, Day 29, Day 43, Day 57, Day 85 and Day 115
SAFETY MEASURES	
 • Adverse events • [REDACTED] • Slit lamp biomicroscopy findings
EFFICACY MEASURES	
 • Lower lid meibomian gland secretion assessment 
 ○ Total meibomian gland score

Clinical Research Protocol

Protocol TRS-008

[figure not shown]
01-Feb-2023

	
• Lid margin erythema

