STATISTICAL CONSIDERATIONS	This is a pilot study to compare the safety and efficacy of two different dosing regimens, BID and TID, of TP-03 for the treatment of MGD. There are no prior data available to perform a sample size estimate. The sample size of 40 participants was selected based on clinical and practical considerations.
STATISTICAL ANALYSIS PLAN	
Safety measures will be summarized for each treatment regimen and both treatment regimens combined using descriptive statistics.
 
Efficacy measures will be compared between dosing regimens as the change from baseline using either the t-test or Wilcoxon rank-sum test as appropriate. Comparisons will be two-sided using an α of 0.05. No adjustment will be made for multiple comparisons.

TABLE OF CONTENTS

1.	ABBREVIATION TABLE.....	7
2.	INTRODUCTION AND RATIONALE.....	8
2.1.	MEIBOMIAN GLANDS	8
2.2.	MEIBOMIAN GLAND DYSFUNCTION	8
2.6.	POTENTIAL RISKS AND BENEFITS	13
3.	TREATMENTS.....	14
3.1.	TP-03 AND VEHICLE	14
4.	STUDY OBJECTIVE.....	15
5.	STUDY DESIGN.....	15
6.	STUDY POPULATION	15
7.	STUDY OUTCOME MEASUREMENTS.....	18
7.1.	EFFICACY PARAMETERS.....	18
7.2.	SAFETY PARAMETERS	18
8.	CLINICAL EVALUATIONS	18
8.1.	DAY 1	18
8.2.	DAYS 15 (± 4 DAYS) AND 29 (± 5 DAYS)	19
8.3.	DAY 43 (-7/+6 DAYS) AND DAY 57 (-7/+10 DAYS).....	20
8.4.	DAY 85 (-13/+7 DAYS).....	20
8.5.	DAY 115 (+60 DAYS)	21
9.	STUDY DRUG	21
10.	STUDY PROCEDURES AND ASSESSMENTS	22
10.1.	INFORMED CONSENT	22
10.2.	PARTICIPANT ID ASSIGNMENT.....	22
10.3.	STUDY TREATMENT COMPLIANCE	23
10.4.	VISIT SCHEDULE AND EXAMS	23
10.5.	STUDY EXIT	23
11.	EARLY TERMINATION AND PARTICIPANT DISCONTINUATION.....	23

12. STATISTICAL CONSIDERATIONS AND ANALYSIS	25
12.1. SAMPLE SIZE	25
12.2. RANDOMIZATION.....	25
12.3. GENERAL CONSIDERATIONS	25
12.4. MISSING DATA	25
12.5. STUDY OUTCOMES	25
12.6. STATISTICAL HYPOTHESES.....	26
12.7. STATISTICAL ANALYSES	26
12.8. INTERIM ANALYSIS	27
12.9. FINAL REPORT	27
13. ETHICAL AND REGULATORY CONSIDERATIONS	27
14. INVESTIGATOR RESPONSIBILITIES.....	28
15. CONCOMITANT MEDICATIONS AND THERAPIES	29
15.1. PROHIBITED CONCOMITANT MEDICATIONS/PROCEDURES	29
16. ADVERSE EVENTS AND SERIOUS ADVERSE EVENTS	30
16.1. DEFINITION OF ADVERSE EVENTS (AE)	30
16.2. DEFINITION OF SERIOUS ADVERSE EVENTS (SAE)	30
16.3. CLASSIFICATION OF AN ADVERSE EVENT	30
16.4. TIME PERIOD AND FREQUENCY FOR EVENT ASSESSMENT AND FOLLOW-UP	32
16.5. ADVERSE EVENT REPORTING.....	33
16.6. SERIOUS ADVERSE EVENT REPORTING.....	33
16.7. REPORTING EVENTS TO PARTICIPANTS	34

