12. STATISTICAL CONSIDERATIONS AND ANALYSIS

12.1. SAMPLE SIZE

There is no prior data available for TP-03 in the treatment of MGD to use as a performance estimate. The sample size of 40 participants was selected based on clinical and practical considerations. Results from this study will be used to inform the design of subsequent studies to demonstrate a therapeutic effect.

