12.3. GENERAL CONSIDERATIONS

The sample size, mean and standard deviation will be presented for continuous analysis variables or, if appropriate, the sample size, median and range. Categorical variables will be presented as the count and percentage for each category. Statistical tests will be two-sided and evaluated at an α of 0.05 unless otherwise specified. No adjustment will be made for multiplicity.

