12.5 STUDY OUTCOMES

Efficacy outcomes for this study will include:

- Total meibomian gland secretion score (MGSS) computed as the sum of the grades for all 15 glands evaluated on the lower eyelid with a range from 0 to 45.

- Lid margin erythema

The primary safety endpoint of this study is incidence of treatment-related adverse events (AE). Descriptive statistics of adverse events will be provided, as will narratives of any serious, unexpected, drug-related AEs. Any clinically meaningful changes in visual acuity or slit lamp biomicroscopy findings will be tabulated.

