12.6. STATISTICAL HYPOTHESES

For the comparisons between dosing regimens, the null hypothesis is the efficacy outcomes for the dosing regimens is equal. The alternative hypothesis is the efficacy outcomes are not equal, ie a two-sided test. The hypothesis can be expressed as follows:

$$H_0: E_1 = E_2$$

$$H_A: E_1 \neq E_2$$

where E_1 and E_2 are the efficacy outcomes for each dosing regimen.

For the analyses of the change from baseline in efficacy outcomes for both treatments combined, the null hypothesis is there is no difference between the baseline and follow-up values. The alternative hypothesis is the follow-up outcome has improved from baseline. The hypothesis can be expressed as follows:

$$H_0: D \leq 0$$

$$H_A: D > 0$$

[figure not shown]
where D is the improvement from baseline (note, for some variables, an improvement may be a decrease from baseline).

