2.2.9.1 Adverse Events

Counts and percentages of subjects who experienced any of the following will be presented: any AE, any drug-related AE, discontinuations of study treatment due to an AE, discontinuations of study participation due to an

CONFIDENTIAL

This document is the property of Clinical Trial Data Services and may not be reproduced without the written permission of the management of Clinical Trial Data Services.

AE, any serious adverse events (SAE), deaths, or drug-related SAEs by dosing regimen and overall. Only those adverse events determined to be treatment emergent (TEAE) will be presented. Treatment emergent adverse events are those events with the date of AE onset being greater than or equal to the first date of dosing. Ocular AEs will be tabulated separately from non-ocular AEs for both TEAEs and SAEs.

Verbatim terms on the case report forms will be linked to preferred terms and related body systems using the MedDRA Coding Dictionary version xx (to be updated at time of DBL) The number and percentage of subjects who experience treatment-emergent adverse events will be tabulated by System Organ Class (SOC) and Preferred Term (PT). Adverse events will be counted only once for a subject within each Preferred Term and System Organ Class; thus, since a subject may have more than one Preferred Term within an SOC, percentages of PT may not sum to the percentage in the SOC. If a subject reports a Preferred Term multiple times with differing severities, only the most severe is counted. If a subject reports a Preferred Term multiple times with differing relationships to study medication, only the one related to study drug is counted. Drug-related adverse events are defined as having a causality rating of definitely or potentially related.

AEs will also be tabulated by severity of the event (mild, moderate or severe) and by Investigator's assessment of relationship to study medication (Definitely related, potentially related or not related). Adverse events judged by the Investigator to be Serious Adverse Events (SAEs), SAEs resulting in death, AEs (regardless of seriousness) that require modification to Study Medication dosing will also be tabulated by SOC and PT by dosing regimen and overall.

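### The irritation clause of the clinical hypothesis has no visible criterion for significance and no visible estimate of the TID minus BID difference

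*SAP*

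**What the plan says.** The Clinical Hypothesis row of the Protocol Summary, repeated in SAP section 1, makes one statement with two parts. TID will improve signs more than BID over 85 days, and it will do so "with no significant increase in ocular irritation". Both parts compare the regimens.

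The efficacy part has formal hypotheses. Protocol 12.6 begins: "For the comparisons between dosing regimens, the null hypothesis is the efficacy outcomes for the dosing regimens is equal". Protocol 12.7 names the tests.

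The safety side is descriptive throughout. The Protocol Summary says: "Safety measures will be summarized for each treatment regimen and both treatment regimens combined using descriptive statistics". SAP 2.2.9 adds: "Only descriptive statistics will be presented; inferential statistical testing will not be performed". Under SAP 2.2.9.1 the outputs are counts and percentages of subjects by regimen and overall, by system organ class and preferred term, with further tables by severity and relationship. It also says: "Ocular AEs will be tabulated separately from non-ocular AEs for both TEAEs and SAEs". Protocol 12.5 makes the incidence of treatment-related adverse events the primary safety endpoint.

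On size, Protocol 12.1 says: "The sample size of 40 participants was selected based on clinical and practical considerations". The Protocol Summary gives 1:1 allocation and up to 40 participants.

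**The concern.** The irritation clause is a claim about a difference between regimens, and nothing visible in the plan estimates that difference. No visible text says whether significant is meant statistically or clinically, or what size of increase would count.

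The design makes the question a natural one. Under Protocol 12.2 everyone receives active drug morning and evening, and only the afternoon bottle differs. The contrast between arms is therefore the effect of the third active drop. Protocol 12.1 says the results will inform later studies.

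Two percentages printed side by side, without an interval and read against a hypothesis of no significant increase, could be taken to show that there was none. At this sample size they could not show that.

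**Working it through.** **The plan's own figure.** N = 40 has no effect size, standard deviation, event rate or power behind it, and Protocol 12.1 says so. There is nothing to reproduce. The check is what 40 participants can say about irritation.

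**Inputs**
- Per arm: 40 / 2 = 20, from the maximum enrolment and 1:1 allocation.
- Two-sided α = 0.05, the general rule in Protocol 12.3, used here only to see what a test would deliver. The plan specifies no safety test.
- Irritation rates: the documents give none, so every rate below is an assumption.

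**Step 1. Would a test help?** Exact power is the sum, over all pairs (x, y), of Bin(x; 20, p_BID) × Bin(y; 20, p_TID), counting only pairs with Fisher p ≤ 0.05.

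| Assumed BID rate | Assumed TID rate | Power |
|---|---|---|
| 5% | 15% | 7% |
| 10% | 20% | 7% |
| 20% | 40% | 19% |
| 10% | 30% | 24% |
| 10% | 50% | 74% |

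For the 10- and 20-point rises in the first four rows, power is 7% to 24%. It reaches 74% only for the 40-point rise in the last row.

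**Step 2. How large an observed excess would still be non-significant?** Take 2/20 on BID and 8/20 on TID. With 10 events among 40 and equal arms, the two-sided Fisher p is twice the lower tail:

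p = 2 × [C(20,0)·C(20,10) + C(20,1)·C(20,9) + C(20,2)·C(20,8)] / C(40,10)
= 2 × (184,756 + 3,359,200 + 23,934,300) / 847,660,528
= 2 × 0.0324 = 0.065.

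An observed fourfold rate would count as not significant. It takes 9/20 to cross the line (p = 0.031).

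**Step 3. What would an interval show?** With Wilson limits (l, u) for each arm and d = p_TID − p_BID, the Newcombe limits are

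lower = d − √[(p_TID − l_TID)² + (u_BID − p_BID)²]
upper = d + √[(u_TID − p_TID)² + (p_BID − l_BID)²].

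The Wilson 95% limits are 0.028 to 0.301 for 2/20 and 0.081 to 0.416 for 4/20.

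- 2/20 in each arm: d = 0, half-width = √(0.072² + 0.201²) = 0.214, so about ±21 points.
- 4/20 TID, 2/20 BID: lower = 0.10 − √(0.119² + 0.201²) = −0.134; upper = 0.10 + √(0.216² + 0.072²) = 0.328. That is −13 to +33 points.
- Equal counts of 0 or 4 per arm give about ±16 or ±25 points.

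**Step 4. Could the pilot show that there is no important increase?** For non-inferiority at one-sided 0.025 and 80% power, with equal true rate p and margin m, n per arm = 2p(1 − p)(1.96 + 0.84)² / m². With an assumed 10-point margin this gives 75, 142 or 252 per arm at rates of 5%, 10% or 20%. With a 20-point margin it gives 19, 36 or 63. Only the most lenient of these six cases fits within 20 per arm.

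**The case against.** The strongest reply is that nothing is wrong with the analysis. Protocol and SAP agree that safety is descriptive, and that is ordinary for a small pilot. Irritation recorded as an adverse event will appear in the separate ocular tables by regimen, and any reader can compute an interval from the counts. The phrase stands under Clinical Hypothesis, not under Statistical Hypotheses. Elsewhere (Protocol 12.5 and 12.7) changes in visual acuity and slit lamp findings are judged by clinical meaning. A clinical reading of significant needs no test.

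Much of this stands. There is no conflict between the two documents, and the ban on safety tests is not itself a defect. What remains is that, on either reading of significant, no visible text says how large an increase would count, and no planned output shows how precisely the difference is known.

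A reader might go further and infer that part of the trial's question cannot be answered, or that the clause is bound to be declared met. The documents do not support either inference. The planned tables do inform on irritation, and they address the stated safety objective and the primary safety endpoint. No visible decision rule declares the clause met. Irritation may also be covered where the text is blacked out or absent: one safety measure is redacted, most of SAP 2.2.8 is not shown, and the visible headings pass from 2.2.9.1.3 to 2.2.9.3. Protocol 12.7 mentions a post-treatment survey, and the abbreviation table lists VAS and SPEED, but their content cannot be seen.

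**Conclusion.** The point holds as a minor one. The hypothesis makes a between-regimen claim about irritation, and the visible plan attaches to it no criterion, no estimate of the difference and no measure of precision. The mismatch is between the wording of the hypothesis and the planned output, in both documents alike.

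A significance test is not the remedy, because non-significance would be the likely result for the assumed 10- and 20-point rises in step 1, even if they were real. An interval is more honest but will be wide, with half-widths of about 16 to 25 points for equal counts of 0 to 4 per arm.

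These figures rest on 20 participants per arm, which is the planned maximum, and on assumed event rates. The conclusion is limited to the visible text: if a redacted or missing section defines irritation and compares it between regimens, less of the point remains.

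**What to change.** Keep safety free of hypothesis tests, and make two changes.

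1. In SAP 2.2.9.1, add the TID minus BID difference in the percentage of participants with ocular irritation TEAEs, with a 95% Newcombe interval. List the preferred terms that count as ocular irritation before any unmasking, including before any interim look under Protocol 12.8 that reveals assignments. State that the interval is descriptive and is not to be read as a test. The two can differ: for 8/20 against 2/20 the Newcombe interval is about +3 to +53 points, although Fisher's p is 0.065.
2. In the clinical hypothesis of both documents, replace the irritation clause with an aim such as *and to estimate the difference in ocular irritation*, so that non-significance is not read as no increase.

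The cost is a short list of terms, one extra table column and one reworded phrase. The downside is that the interval will show openly how little 40 participants can say about added irritation.
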